7.7.1 Criteria for Positive Blood Culture for Eligibility

For study eligibility, subjects must have blood culture positive for SA determined by rapid diagnostic or conventional method from blood culture specimens collected within 72 hours prior to randomization. Time of positive blood culture starts from when specimen is collected for blood culture. The site microbiological laboratory is encouraged to use a Food and Drug Administration (FDA)-cleared, European Conformity-in vitro diagnostic certified, or Sponsor-approved rapid diagnostic test to identify SA if it is available at the site. Subjects may be enrolled based on a positive result from a rapid diagnostic test, but confirmation of SA by conventional culture methods will be the required objective measure for SA in the study analyses for efficacy. Subjects who are enrolled based on a positive rapid diagnostic test, but have negative blood culture result for SA, will discontinue study drug if the Investigator decides to discontinue antibiotic treatment of SAB. In the event subjects will complete the EOT for the study drug safety evaluations and have additional safety follow-up 7 days after last dose in person, if feasible, or by phone.

The study site's local microbiology laboratory will perform identification and in vitro susceptibility testing to standard of care antibiotics according to local practices for all blood cultures positive for SA. The Investigator should ensure that all SA isolates obtained from all cultures performed during the study period (and wherever possible, the isolate from the initial positive culture for SA) are sent to the central microbiology laboratory, as described in the Laboratory Manual. The local microbiology laboratory will be required to prepare SA isolates for shipment to the central microbiology laboratory as outlined in the Laboratory Manual. Although only SA isolates should be sent to the central microbiology laboratory, all organisms isolated from blood cultures performed during the study should be recorded in the electronic data capture (EDC) system. The central microbiology laboratory will confirm the identification and perform in vitro susceptibility testing and phage susceptibility of isolates in batches for the purposes of the final study analysis; the central microbiology laboratory will not be providing results to the sites. Further evaluation to identify the potential mechanism of resistance may be performed.

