## 3.2 Analysis Populations

### 3.2.1 Intent-to-Treat Population (Efficacy Population 1)

The Intent-to-Treat (ITT) Population is defined as all randomized subjects in Phase 1b and Phase 2a who receive at least 1 dose of study drug. This will not include individuals that screen failed or were randomized but did not receive phage or placebo - at least one dose of phage or placebo must have been received.

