### 3.2.2 Per Protocol Microbiological Intent-to-Treat (MITT) Population (Efficacy Population 2)

The Per Protocol MITT Population is defined as all subjects in the ITT population and enrolled in Phase 2a with baseline SAB and who receive at least 4 initial doses of study drug (placebo or phage). All protocol deviations for inclusion and exclusion will be determined prior to database lock and documented in the TMF.

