### 3.4 Efficacy Assessment

Efficacy data will be analyzed for ITT population, Per Protocol MITT population, Phage Persistence and Clearance population, and Phage-Sensitivity ITT population (if needed):

- Efficacy analysis performed using ITT population and Phase-Sensitivity ITT population (if needed) will be summarized by pooled treatment versus pooled placebo for Phase 1b and Phase 2a:
  - Phase 1b (uncomplicated SAB) vs Phase 1b placebo
  - Phase 2a (complicated SAB) vs Phase 2a placebo
- Efficacy analysis performed using Per Protocol MITT population will be summarized by pooled treatment versus pooled placebo for Phase 2a:
  - Phase 2a vs Phase 2a placebo.
- Efficacy analysis performed using Phage Persistence and Clearance population will be summarized by following:
  - Combination of Phase 1b (excluding cohort 1) and Phase 2a Persistence vs Combination of Phase 1b (excluding cohort 1) and Phase 2a Clearance vs Combination of Phase 1b placebo (excluding cohort 1) and Phase 2a placebo
  - Phase 2a Persistence vs Phase 2a Clearance vs Phase 2a placebo

Combination of Phase 1b placebo (excluding cohort 1) and Phase 2a placebo includes Phase 1b placebo (excluding cohort 1) and Phase 2a placebo in the ITT population. Phase 2a placebo includes Phase 2a placebo in the ITT population.

Phage Persistence and Phage Clearance Population and Phage-Sensitivity ITT population (if needed) will be reported by the Sponsor separately. Subject lists for Phage Persistence and Phage Clearance Population and Phage-Sensitivity ITT population (if needed) will be provided by Sponsor for analysis.

The endpoints in section 3.4.1 for Phase 1b and Phase 2a may be assessed as secondary endpoints.

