**Table 3. Microbiological Outcome**

Category	Criteria
Eradication	Blood cultures negative for SA for 2 consecutive days.
Presumed eradication	Follow-up blood cultures were not done (or were technically uninterpretable) and the subject has responded clinically, as defined in Table 2 of protocol .
Persistence	Follow-up blood cultures do not meet the criteria for eradication and are positive for SA either daily or every other day.
Presumed persistence	Follow-up blood cultures were not done (or were technically uninterpretable) and the subject has not responded clinically, as defined in Table 2 of protocol .
Recurrence	A positive blood culture for SAB at any time after documented eradication or presumed eradication.

In [Table 3](#), “the subject has responded clinically” indicates that the subject experiences clinical improvement or response per investigator’s assessment at EOT for study drug. Any 2 consecutive assessments with blood cultures negative for SA is assigned as Eradication programmatically, no matter if these 2 assessments are consecutive days or consecutive visits.

Time to first resolution of any signs/symptoms related to focal site of SA infection (e.g., joint pain; redness; swelling; weight-bearing, back pain; weight-bearing, skin redness; drainage) from randomization on Day 1 will be analyzed. If all signs/symptoms are absent, the subjects will be considered achieving the resolution of signs/symptoms related to focal site of SA infection. If any signs/symptoms are present during the study assessments, the subjects will be censored at the date of latest assessment of signs/symptoms assessments for focal site of SA infection.

Time-to-event (days) = Censoring date/date of first resolution assessment – date of first dose of study drug + 1

The Kaplan-Meier method will be used to estimate the 25%, median and 75% times. The hazard ratio, 95% confidence interval (CI) of hazard ratio, and p-value from Cox regression model will be provided to compare AP-SA02 and placebo. Cox regression will include treatment (AP-SA02 and placebo) as factor. All assessments from scheduled and unscheduled visits will be included in the time-to-event analysis.

The Kaplan-Meier plot of time to first resolution of any signs/symptoms related to focal site of SA infection will be provided.

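### The SAP counts never culture-positive subjects as eradicated or resolved in its ITT and Persistence/Clearance sets, although the protocol requires culture confirmation for efficacy

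*Protocol*

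**What the plan says.** **Protocol.** Section 7.7.1 states that "Subjects may be enrolled based on a positive result from a rapid diagnostic test", but also that "confirmation of SA by conventional culture methods will be the required objective measure for SA in the study analyses for efficacy". It foresees discordant results: subjects enrolled on a rapid test who "have negative blood culture result for SA, will discontinue study drug if the Investigator decides to discontinue antibiotic treatment of SAB". Stopping is conditional, so some culture-negative subjects may complete dosing. Section 9.1 defines MITT, which requires baseline SAB, for both phases. Section 7.2 ties the first three Phase 2a endpoints to it.

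**SAP populations.**
- ITT (3.2.1, Efficacy Population 1) is "all randomized subjects in Phase 1b and Phase 2a who receive at least 1 dose of study drug".
- Per Protocol MITT (3.2.2) is "all subjects in the ITT population and enrolled in Phase 2a with baseline SAB", plus at least four initial doses. Section 3.1.2 defines baseline SAB by blood culture.
- Persistence/Clearance (3.2.3) needs one PK sample and four initial doses. Its pooled placebo group (3.4) "includes Phase 1b placebo (excluding cohort 1) and Phase 2a placebo in the ITT population".
- Phage-Sensitive ITT (3.2.4) needs an SA isolate. Section 3.3.3 accepts isolates from any visit, and 3.4 makes the analysis conditional on need.

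**SAP endpoint rules.** The note to Table 3 in 3.4.1 says: "Any 2 consecutive assessments with blood cultures negative for SA is assigned as Eradication programmatically". Section 3.6 defines initial resolution as two consecutive days of negative cultures and lets Day 1 pre-dose cultures count. Late composite efficacy (2.3.2) is survival at EOS without microbiological failure. None of these rules asks for an earlier positive culture.

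**The concern.** A subject with no culture-proven bacteremia has nothing to eradicate. In the ITT and Persistence/Clearance tables the rules nevertheless convert an absence of positive cultures into a favorable microbiological result. Eradication rates then partly measure how often the rapid test was not confirmed by culture.

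Phase 1b is the most exposed. The SAP adds efficacy tables for it (Section 6, item 4) but confines Per Protocol MITT to Phase 2a, so no Phase 1b set requires a culture-confirmed baseline. Section 6 lists the changed population definitions without mentioning the 7.7.1 requirement.

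**Working it through.** **1. Following one subject through the rules.** Take a subject who is rapid-test positive, has no SA-positive conventional culture at any time, and receives at least one dose.

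- ITT: included. Persistence/Clearance: included if a PK sample is drawn and four initial doses are given. A placebo subject enters that comparison through ITT. Per Protocol MITT: excluded.
- Microbiological outcome: two consecutive negative assessments give Eradication, which Protocol 7.8 counts as favorable.
- Time to initial resolution: the event is dated at the first of two consecutive negative days, minus first-dose time. If the first negative is the Day 1 pre-dose culture, the time is zero or below.
- Microbiological failure or relapse: every limb needs a positive culture, so none is met.
- Late composite: success if the subject is followed to EOS and alive.
- Clinical response (Protocol Table 2): the culture limb is met. Survival, no new foci or complications, and resolved signs and symptoms are still required.

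**2. The plan's own figure.** Inputs from SAP 2.2.4: N = 42, 2:1, 90% meeting MITT, 30% response on placebo, a 50-point difference (so 80% on AP-SA02), one-sided 0.05, Fisher's exact test. 42 × 0.90 = 37.8, about 38. Full binomial enumeration at 25:13 gives 87.8% power, so the stated minimum of 80% is met. The present point does not depend on this figure.

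**3. Effect on arm rates (illustration).** The documents give no eradication rates, so the planned clinical rates of 30% and 80% stand in for them. Let f be the assumed share of never culture-positive subjects, equal in both arms and all scored as successes.

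Observed rate = p(1 − f) + f; difference = (0.80 − 0.30)(1 − f).

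| f | About, of 42 | Placebo | AP-SA02 | Difference (points) | Power, 28:14, one-sided Fisher |
|---|---|---|---|---|---|
| 0 | 0 | 30.0% | 80.0% | 50.0 | 90.8% |
| 2.5% | 1 | 31.8% | 80.5% | 48.8 | 89.3% |
| 5% | 2 | 33.5% | 81.0% | 47.5 | 87.6% |
| 10% | 4 | 37.0% | 82.0% | 45.0 | 83.9% |

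Other assumed rates show the same pattern. With 15/25 (60.0%) against 4/13 (30.8%), the difference is 29.2 points. Adding three automatic successes on active and one on placebo gives 18/28 (64.3%) against 5/14 (35.7%), a difference of 28.6 points. Both arms rise while the difference hardly moves.

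**4. Chance imbalance (28:14, same 30% and 80%).**
- One such subject, on active: (27 × 0.80 + 1)/28 = 80.7%; difference 50.7 points.
- One, on placebo: (13 × 0.30 + 1)/14 = 35.0%; difference 45.0 points.
- Two, both on placebo: (12 × 0.30 + 2)/14 = 40.0%; difference 40.0 points.

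**5. Phase 1b.** Two planned cohorts of four at 3:1 give 6 active and 2 placebo. One subject carries 1/6 = 16.7 points of the active rate or 1/2 = 50 points of the placebo rate.

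**6. Bound on the number.** The 10% allowance (about 4 of 42) covers every reason for failing MITT as the protocol defines it, including subjects never dosed, whom SAP ITT already excludes. Under SAP 3.1.2 a subject can also fail baseline SAB on timing alone, with a positive culture taken more than 72 hours before first dose. Such a subject is culture-positive. On the plan's own assumption, the affected share of ITT is therefore below 10%.

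**The case against.** The strongest reply is that 7.7.1 names culture as the measure of SA and does not say that every efficacy population must exclude culture-negative subjects. The SAP does rest its microbiological endpoints on local cultures. The protocol's own ITT has no culture condition, and its Table 5 requires no earlier positive. This stands in part: the gap is partly inherited, and an ITT set that keeps all dosed subjects is not itself an error. It does not rescue the endpoint rules, under which a subject without the required confirmation is scored as eradicated. The SAP also widened the gap by accepting any two consecutive assessments as well as consecutive days, and by dropping MITT for Phase 1b.

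Further points that stand:
- Phase 1b efficacy is described as exploratory and unpowered, and SAP 3.1.4 plans no formal testing.
- SAP 3.3.4 tabulates randomization on rapid testing, so readers will see that count.
- Phage-Sensitive ITT covers Phase 1b and needs an isolate, although not a baseline one.
- Counting Day 1 pre-dose cultures also affects culture-positive subjects who cleared early. That is a separate question.

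A reader might infer more than the documents support:
- *Late-composite success is automatic.* For subjects who stop under 7.7.1, that section describes EOT safety evaluations and follow-up 7 days after the last dose, with no EOS data. Some may also miss the four-dose threshold for Persistence/Clearance.
- *These subjects are scored as clinical cures.* Clinical response has other limbs and is assessed by both the investigator and the CEAC.
- *The active arm is favored.* With balanced numbers the difference shrinks.

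**Conclusion.** The point holds as a defect in the endpoint rules. In ITT and Persistence/Clearance, including its placebo group, a never culture-positive subject is counted as eradicated or resolved and, if followed to EOS alive, as a late-composite success. Phase 1b has no set that requires a culture-confirmed baseline.

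The size is modest and uncertain. Arm-level eradication rates rise. A balanced share of 2.5% to 10% takes a 50-point difference to between 48.8 and 45.0 points, and imbalance can move it either way. These figures rest on borrowed clinical rates, an assumed share, and automatic success for each such subject. Four of 42 should not be read as the expected number.

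The Phase 2a Per Protocol MITT tables are unaffected. The documents do not support reading this as a flaw in the whole efficacy analysis.

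**What to change.** In SAP 3.4.1 and 3.6, require at least one SA-positive conventional blood culture from a specimen collected before first dose before any of the following can be assigned: Eradication, presumed eradication, initial resolution, absence of microbiological failure or relapse, or late composite success. The eligibility culture or any later pre-dose culture should qualify. Do not limit it to the 3.1.2 window of 72 hours before first dose: eligibility counts 72 hours back from randomization, and the narrower window could drop truly bacteremic subjects.

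Show other subjects as not applicable for these endpoints in ITT and in Persistence/Clearance, including its placebo group. Report the Phase 1b microbiological endpoints in culture-confirmed subjects.

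Keep all dosed subjects for clinical response, NEWS2, death, hospital and safety endpoints. Add a sensitivity table of clinical response that excludes subjects without culture confirmation. Restricting clinical response itself throughout ITT would be a trade-off and is not proposed.

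The cost is a few sentences, one extra table and a few fewer subjects in the ITT microbiological tables. No new data are needed. The condition uses only specimens taken before dosing, so treatment cannot influence who is set aside.

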7.7.2 Cultures From Sterile Sites

Specimens from sterile sites (eg, joint fluid, tissue) will be collected as clinically indicated and sent to the site's local microbiology laboratory for culture and susceptibility per standard practice. Results of the cultures will be entered into the EDC system. Isolates of all SA isolates will be sent to the central microbiology laboratory for confirmation of identification and susceptibility testing as outlined in the Laboratory Manual.

7.8 Microbiological Outcome

Microbiological response will be determined programmatically as 1 of the following outcomes based on the results of blood cultures and/or urine cultures at EOT for study drug (Day 5), TOC for study drug (Day 12), TOC for BAT, and EOS. A microbiological favorable assessment will include eradication and presumed eradications, as detailed in [Table 5](#).

Table 5. Microbiological Outcome

Category	Criteria
Eradication	Blood cultures negative for SA for 2 consecutive days.
Presumed eradication	Follow-up blood cultures were not done (or were technically uninterpretable) and the subject has responded clinically, as defined in Table 2 .
Persistence	Follow-up blood cultures do not meet the criteria for eradication and are positive for SA either daily or every other day.
Presumed persistence	Follow-up blood cultures were not done (or were technically uninterpretable) and the subject has not responded clinically, as defined in Table 2 .
Recurrence	A positive blood culture for SAB at any time after documented eradication or presumed eradication.
SA = Staphylococcus aureus ; SAB = Staphylococcus aureus bacteremia.	

7.9 Pharmacokinetic Assessments

PK samples for AP-SA02 will be collected from subjects enrolled at predetermined/qualified PK sites on the following days and times, and evaluated based on AP-SA02 levels as measured by venous blood samples:

- Day 1: pre-dose (-60 minutes) and , 0.5 hours (± 15 minutes), 1 hour (± 15 minutes), and 3 hours (± 15 minutes) post first dose of the day;
- Days 2 to 4: 1 sample 1 hour (30 minutes) post first dose of the study day;
- Day 5: 1 hour (± 15 minutes) post last dose of the day; and
- Day 6: 24 hours (± 30 minutes) post last dose.

PK parameters of AP-SA02 will be assessed from subjects enrolled at predetermined/qualified PK sites with serial PK sampling, including maximum observed plasma concentration (C_{max}), time to reach C_{max} (T_{max}), terminal elimination half-life ($t_{1/2}$), CL, volume of distribution (V_z), area under the plasma concentration-time curve (AUC) from time 0 to the last quantifiable time (AUC_{0-t}), and AUC from time 0 to infinity ($AUC_{0-\infty}$). Additional details regarding PK analysis methodology will be described in the Statistical Analysis Plan (SAP).

7.10 Pharmacodynamic Assessments

Pharmacodynamics will be evaluated based on the following:

- Time to resolution of signs/symptoms of bacteremia present at Screening;
- Time to resolution of bacteremia based on blood cultures; and/or
- Change in CRP from baseline.

8 SAFETY ASSESSMENTS

Safety will be assessed by monitoring AEs, vital signs, laboratory data (chemistries, hematology, and coagulation), immunogenicity evaluation, physical examinations, ECGs, and radiologic imaging per standard of care (eg, echocardiogram).

8.1 Adverse Events

An AE is defined as any untoward medical occurrence in a clinical investigation subject administered a pharmaceutical product, which does not necessarily have a causal relationship with this treatment. An AE can therefore be any unfavorable and/or unintended sign (including an abnormal laboratory finding), symptom, or disease temporally associated with the use of an investigational medicinal product, whether or not related to the investigational medicinal product. All AEs, including observed or volunteered problems, complaints, or symptoms, are to be recorded on the appropriate eCRF.

AEs, which include clinical laboratory test variables, will be monitored and documented from the time of informed consent. Subjects should be instructed to report any AE that they experience to the Investigator, whether or not they think the event is due to study treatment. Beginning at Screening, Investigators should make an assessment for AEs at each visit and record the event on the appropriate AE eCRF.

Wherever possible, a specific disease or syndrome rather than individual associated signs and symptoms should be identified by the Investigator and recorded on the eCRF. However, if an observed or reported sign or symptom is not considered a component of a specific disease or syndrome by the Investigator, it should be recorded as a separate AE on the eCRF. Additionally, the condition that led to a medical or surgical procedure (eg, surgery, endoscopy, tooth extraction, or transfusion) should be recorded as an AE, not the procedure itself.

Any medical condition already present at Screening should be recorded as medical history and not be reported as an AE unless the medical condition or signs or symptoms present at baseline changes in severity, frequency, or seriousness at any time during the study. In this case, it should be reported as an AE.

Clinically significant abnormal laboratory or other examination (eg, ECG) findings that are detected during the study or are present at Screening and significantly worsen during the study should be reported as AEs, as described below. The Investigator will exercise his or her medical and scientific judgment in deciding whether an abnormal laboratory finding or other abnormal assessment is clinically significant. Clinically significant abnormal laboratory values occurring during the clinical study will be followed until repeat tests return to normal, stabilize, or are no longer clinically significant. Abnormal test results that are determined to be an error should not be reported as an AE. Laboratory abnormalities or other abnormal clinical findings (eg, ECG abnormalities) should be reported as an AE if any of the following are applicable:

- If an intervention is required as a result of the abnormality;
- If action taken with the study drug is required as a result of the abnormality; or
- Based on the clinical judgment of the Investigator.

8.1.1 Adverse (Drug) Reaction

All noxious and unintended responses to a medicinal product related to any dose should be considered an adverse drug reaction. “Responses” to a medicinal product means that a causal relationship between a medicinal product and an AE is at least a reasonable possibility, ie, the relationship cannot be ruled out.

8.1.2 Unexpected Adverse Drug Reaction

An Unexpected Adverse Drug Reaction is defined as an adverse reaction, the nature or severity of which is not consistent with the applicable product information. For AP-SA02, the reference safety information is included in the Investigator’s Brochure currently in force. The reference safety information will be reviewed yearly and the periodicity of the review will be harmonized with the reporting period of the Development Safety Update Report.

